3.2. Treatment Groups and Duration

Subjects entering with a PGA ≥ 1 will receive treatment with tapinarof cream, 1% until they achieve a PGA score of 0, at which time treatment will be discontinued and subjects monitored for durability of response. If or when disease worsening occurs, as evidenced by a PGA ≥ 2 , treatment will then be re-initiated and continued until a PGA of 0 is observed. Subjects entering with a PGA of 0 will have treatment discontinued and be monitored for durability of response. If/when disease worsening occurs, as evidenced by a PGA ≥ 2 , treatment will then be re-initiated and continued until a PGA of 0 is observed. (Section [5.1.5.2](#)).

A subject will be considered to have completed the study when he/she completes all required procedures/visits for the 40-week (Visit 11) treatment period. The end of the study is defined as when the last active subject has completed the Follow-up Visit.

4. STUDY POPULATION

4.1. Type and Number of Subjects

Approximately 850 subjects who completed pivotal Study DMVT-505-3001 or pivotal Study DMVT-505-3002 will be enrolled in this study at approximately 100 to 120 study sites in the US and Canada.

Protocol violations from inclusion and exclusion criteria are prohibited because ineligible study subjects can potentially jeopardize the scientific integrity of the study, regulatory acceptability, or subject safety. Therefore, adherence to the criteria as specified in the protocol is essential.

4.2. Inclusion Criteria

Each subject must meet all of the following criteria to be eligible to be enrolled in this study:

1. Completed the 12-week treatment period in 1 of the 2 pivotal studies (Study DMVT-505-3001 or Study DMVT-505-3002)
2. Male or female
3. Female subjects of child-bearing potential and male subjects who are engaging in sexual activity that could lead to pregnancy should use one of the following acceptable birth control methods while on study and for 4 weeks after the last exposure to study drug. Acceptable contraception methods are:
 - Female subject or male subject's female partner is surgically sterile (bilateral tubal ligation, hysterectomy, bilateral oophorectomy) for a minimum of 3 months prior to the first dose of study drug
 - Female subject or male subject's female partner has had an intrauterine device in place for at least 3 months prior to the first dose of study drug
 - Double barrier methods (e.g., condom plus diaphragm, condom or diaphragm plus spermicide) starting at least 14 days prior to the first dose of study drug
 - Subjects who claim abstinence as their method of contraception are allowed provided they agree to use a double barrier method (e.g., condom plus diaphragm, condom or diaphragm plus spermicide) should they become sexually active from Screening to 1 month after the last dose of study drug
 - Surgical sterilization of male subject or female subject's partner (vasectomy) a minimum of 3 months prior to first dose of study drug
 - Female subject or male subject's female partner is taking hormonal contraceptives starting at least 3 months prior to the first dose of study drug. If hormonal contraceptives were started less than 3 months prior to the first dose of study drug, subjects must agree to use a double barrier method (e.g., condom plus diaphragm, condom or diaphragm plus spermicide) from Screening through 3 months after the initiation of hormonal contraceptives

These allowed methods of contraception are only effective when used consistently, correctly and in accordance with the product label. The Investigator is responsible for ensuring that subjects understand how to properly use these methods of contraception.

Non-CBP is defined as premenarchal or premenopausal females with a documented bilateral tubal ligation, bilateral oophorectomy (removal of the ovaries) or hysterectomy, or hysteroscopic sterilization; or postmenopausal females defined as a cessation of menses for at least 12 months without an alternative medical cause. In questionable cases a blood sample with simultaneous follicle stimulating hormone (FSH) >40 ml/U is confirmatory. Documented verbal history from the subject is acceptable.

Female subjects of CBP must have a negative urine pregnancy test at Baseline (Day 1), as collected from Week 12 of 1 of the 2 pivotal studies (Study DMVT-505-3001 or Study DMVT-505-3002).

4. Capable of giving signed informed consent, as applicable, which includes compliance with the requirements and restrictions listed in the informed consent form (ICF); written informed consent must be obtained prior to any study related procedures.

4.3. Exclusion Criteria

Any subject who meets any of the following criteria will be ineligible to be enrolled in this study:

1. Used a prohibited concomitant product or procedure to treat psoriasis during pivotal study
2. Had an SAE that was potentially related to treatment or experienced an AE that led to permanent discontinuation of treatment in the pivotal study
3. History of or ongoing serious illness or medical, physical, or psychiatric condition(s) that, in the Investigator's opinion, may interfere with the subject's completion of the study
4. Known hypersensitivity to tapinarof or excipients

4.4. Lifestyle Restrictions

Subjects should avoid prolonged exposure to natural or artificial sources of ultraviolet (UV) radiation (e.g., sunlight or tanning booth) and UV light therapy during this study, because UV light may affect the subject's psoriasis. The use of sunscreen on nonlesional areas is allowed.

4.5. Screening Failure

Screen failures are defined as subjects who consent to participate in the clinical study but are not subsequently enrolled. A minimal set of screen failure information is required to ensure transpivotal reporting of screen failure subjects to meet the Consolidated Standards of Reporting Trials publishing requirements and to respond to queries from regulatory authorities. Minimal information includes demography, screen failure details, eligibility criteria, and any SAEs. These data will also be linked to subject data from the initial study.

4.6. Withdrawal Criteria

A subject may voluntarily discontinue treatment and/or withdraw from participation in this study at any time at his/her own request, or may be discontinued from study treatment at any time at the discretion of the Investigator for safety, behavioral, compliance, or administrative reasons. Subjects withdrawn from the study will not be replaced.

4.6.1. Reasons for Withdrawal from Study

Study drug will be discontinued for any of the following reasons:

- Subject has an AE that is considered to be related to study drug or procedures AND is severe enough to warrant treatment discontinuation, as determined by the Investigator (Section 8.1)
- Subject requires concurrent prohibited concomitant medication during the study. If, in the opinion of the Investigator and the study Medical Monitor, such medication will not interfere with the conduct or interpretation of the study or compromise the safety of the subject, then the subject may continue to receive study drug. If the subject is discontinued from study drug, they may remain in the study for safety assessments as needed, at the discretion of the Investigator and Medical Monitor.
- Pregnancy
- Any Grade 3 or 4 AE considered causally related to study drug (Section 8.2.2)

Study drug may be discontinued for any of the following reasons:

- Subject noncompliance
- Investigator noncompliance
- Discontinuation of the study at the request of the Sponsor, regulatory agency, or an Institutional Review Board (IRB)/Independent Ethics Committee (IEC)

If a subject meets a withdrawal criterion during treatment, an Early Termination Visit will be required (Section 7.7).

4.6.2. Temporary Discontinuation

A subject will discontinue study drug when the Investigator determines a PGA of 0 has been achieved as described in Section 5.1.5.1. While actively treating an episode of disease worsening or during the treatment course for a PGA ≥ 2 , there are no specific provisions for temporary discontinuation of treatment during this study, with the exception of the interruption of study treatment for skin irritation (see Section 1.3). If study treatment is interrupted due to a safety issue, the Medical Monitor will be contacted and the event documented in the electronic case report form (eCRF).

4.6.3. Withdrawal Procedures

The primary reason for the discontinuation of study drug and/or withdrawal from study must be recorded in the source document and on the eCRF. If a subject is prematurely discontinued from study drug(s), the Investigator must make every effort to perform an Early Termination Visit (Section 7.7) and document the primary reason for withdrawal.

Should a subject fail to attend a required study visit, the site should attempt to contact the subject and re-schedule the missed visit as soon as possible. The site should also counsel the subject on the importance of maintaining the assigned visit schedule and ascertain whether the subject wishes to and/or should continue in the study based on previous non-compliance. In cases where the subject does not return for the rescheduled visit or cannot be reached to reschedule the

missed visit, the site should make every effort to regain contact with the subject so that they can appropriately be withdrawn from the study with a primary reason of “Lost to Follow-up.”

4.7. Lost to Follow-up

A subject will be considered lost to follow-up if he/she repeatedly fails to return for scheduled visits and is unable to be contacted by the study site. The following actions must be taken if a subject fails to return to the clinic for a required study visit:

- The site must attempt to contact the subject and reschedule the missed visit as soon as possible and counsel the subject on the importance of maintaining the assigned visit schedule and ascertain whether or not the subject wishes to and/or should continue in the study.
- Before a subject is deemed lost to follow-up, the Investigator or designee must make every effort to regain contact with the subject (where possible, 3 telephone calls and, if necessary, a certified letter to the subject’s last known mailing address or local equivalent methods). These contact attempts should be documented in the subject’s medical record.
- Should the subject continue to be unreachable, he/she will be considered to have withdrawn from the study with a primary reason of lost to follow-up.

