11. STATISTICAL EVALUATION

11.1 Subject Disposition

Subjects who enroll (ITT population), who apply any study medication, who complete the study and who withdraw from the study (together with the reasons for withdrawal) will be summarized by counts and percentages. Subjects for whom drug was permanently withdrawn or interrupted due to AE, PGA score or other reasons will also be summarized by counts and percentages, over the entire study and by visit.

Counts will be presented overall and by DB treatment group. Listings by subject will document enrollment and disposition.

The number of days in the study, defined as date of study completion / discontinuation (or date of last visit if the study completion/discontinuation date is missing) minus date of Visit 1 plus 1, will be summarized using descriptive statistics overall and by DB treatment group. A figure with Kaplan-Meier curves will also be generated to illustrate this information.

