11.7 Efficacy Endpoints

Efficacy endpoints are as follows:

For subjects entering the study with a PGA score of clear (0):

- Proportion of subjects who experience PGA ≥ 2 at least 1 time during the study.
- Proportion of subjects who never experience PGA ≥ 2 throughout the study.
- Time to first worsening (PGA ≥ 2), defined as days from date of Visit 1 date to the date of first occurrence of PGA ≥ 2 . Subjects who never experience PGA ≥ 2 throughout the study will be censored at the date of their last PGA assessment.

For subjects entering the study with a PGA score ≥ 1 :

- Proportions of subjects who achieve PGA = 0 at least 1 time during the study

• [REDACTED]

• [REDACTED]

[REDACTED]

For subjects entering the study with a PGA score ≥ 2 :

- Proportions of subjects who achieved PGA = 0 or 1 at least 1 time during the study.
- Proportions of subjects who never achieve PGA = 0 or 1 throughout the study.

The following endpoints will be summarized over subjects in ITT population:

- Duration (days) of treatment episodes, defined as time (days) from the date of each PGA ≥ 2 (or PGA ≥ 1 for the first episode) to 1 day before each subsequent treatment success (PGA = 0). The date of the last PGA assessment will be used as the end date for episodes ongoing at the end of the study.

- [REDACTED]
- [REDACTED] \geq [REDACTED]
- [REDACTED]
- [REDACTED]
- [REDACTED]
- [REDACTED] change and percent change from baseline in %BSA affected by visit (OC and LOCF).
- [REDACTED] change and percent change from baseline in PASI score by visit (OC and LOCF)
- [REDACTED] \geq [REDACTED]
- [REDACTED] \geq [REDACTED]
- [REDACTED] \geq [REDACTED]

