11.11.1 Adverse Events

AE terms will be coded using Medical Dictionary for Regulatory Activities (MedDRA) dictionary. All AEs reported in current study are considered as treatment-emergent AE (TEAE) except for those AEs ongoing at the end of pivotal studies but resolved prior to the Visit 1 date in the extension study.

All TEAEs will be listed by subject, detailing the verbatim term given by the investigator, the preferred term (PT), system organ class (SOC), onset date and time, end date and time, ongoing at the end of pivotal studies (Y/N), duration (days), CTCAE grade, outcome, relationship to study drug, action taken with study drug, other action taken to treat the event, AE of special interest (Y/N), seriousness and criteria for seriousness.

AEs resolved prior to the Visit 1 date, Serious TEAEs (STEAEs), TEAEs leading to study discontinuation and TEAEs related to study drug will also be listed separately. The following adverse events of special interest (AESIs) will be identified and listed separately: contact dermatitis, folliculitis, and headache.

The number and percent of subjects with TEAEs will be summarized as incidence rates of:

- Any TEAE
- Any TEAE Excluding Those Ongoing at the end of the Pivotal Studies
- Any TEAE Ongoing at the end of the Pivotal Studies
- Any treatment-emergent AESIs
- Any treatment-emergent AESIs Excluding Those Ongoing at the end of the Pivotal Studies
- Any treatment-emergent AESIs Ongoing at the end of the Pivotal Studies
- Any treatment-related TEAE
- Any TEAE leading to study drug discontinuation
- Any TEAE leading to study discontinuation
- Any serious TEAE

- Death
- Treatment-related Serious TEAE
- Serious TEAE leading to study drug discontinuation
- Serious TEAE leading to study discontinuation
- TEAE (COVID-19)

Individual PTs will be summarized by SOC in alphabetical order and PT in descending order of frequency for the following subsets and subgroupings:

- All TEAEs
- All TEAEs by maximum CTCAE grade
- All TEAEs by maximum causality (not related, related) to the study drug
- All TEAEs Excluding Those Ongoing at the End of the Pivotal Studies
- All TEAEs ongoing at the end of the pivotal studies
- All treatment-related TEAEs
- All TEAEs leading to study discontinuation
- All TEAEs leading to study drug discontinuation
- All serious TEAEs

All TEAEs and all serious TEAEs will also be summarized by SOC (alphabetical order) and PT (descending order) for the following subgroups:

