- Age (<65 and \geq 65 years old)
- Sex
- Race (White, Other)

Furthermore, TEAEs will be categorized by day of onset among the following 4 categories:

- \leq 12 weeks
- >12 to \leq 24 weeks
- >24 to \leq 40 weeks
- >40 weeks.

For each of these categories, TEAEs will be summarized by SOC in alphabetical order and PT in descending order of frequency. TEAEs ongoing at the end of the pivotal studies will be considered in the first category (i.e. day of onset \leq 12 weeks).

At each level of summarization, a subject will be counted once if he/she reported one or more events. The severity of TEAEs and relationship to study drug will be summarized in a similar

manner. For summaries of relationship to study drug, a subject will be classified according to the closest relationship. For summaries of TEAE CTCAE grade, a subject will be classified according to the worst grade.

For AESIs, summarization will be more extensive, reflecting the more detailed information collected. Information summarized will include number of events per subject, earliest onset day, duration (in days), causality, grade and seriousness of AESIs, outcome, actions taken, assorted physical characteristics of the AESIs, and demographic/baseline characteristics and PGA status of the subjects experiencing them. Each type of AESI will be summarized separately. If a subject has more than one treatment-emergent occurrence of an AESI, the subject's maximum duration, highest levels of causality and seriousness, maximum grade and generally the most extreme level of each characteristic will be summarized. If an AESI was ongoing at end of study (EOS), it will not be included in the duration summary. AESIs ongoing at the end of pivotal studies will also be included in the summary.

A Kaplan-Meier figure will be generated for each AESI of time to first event for events starting during the study. Subjects not experiencing the AESI will be censored at the date of study completion or discontinuation. AESIs ongoing at the end of pivotal studies will not be included.

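### AESI Kaplan-Meier figures censor at a discontinuation date that is undefined for lost-to-follow-up subjects and may fall weeks after the last AE assessment

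*Protocol*

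**What the plan says.** **When a subject counts as lost.** Protocol 4.7 has a subject "considered lost to follow-up if he/she repeatedly fails to return for scheduled visits and is unable to be contacted by the study site". Before that status is given, the site must try to regain contact: "where possible, 3 telephone calls and, if necessary, a certified letter to the subject’s last known mailing address", or a local equivalent. Then: "Should the subject continue to be unreachable, he/she will be considered to have withdrawn from the study with a primary reason of lost to follow-up". No number of missed visits, no time limit and no effective date of withdrawal is given. Scheduled visits are 4 weeks apart (Protocol 3.1).

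**When AEs are observed.** Protocol 6.3.1 collects AEs up to the final visit or contact. Protocol 8.1 has subjects asked about AEs at each visit or contact.

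**How AESIs are analysed.** SAP 11.11.1 plans two kinds of output:
- Counts: "The number and percent of subjects with TEAEs will be summarized as incidence rates of" a list of categories that includes AESIs.
- Curves: "A Kaplan-Meier figure will be generated for each AESI of time to first event for events starting during the study", with this censoring rule: "Subjects not experiencing the AESI will be censored at the date of study completion or discontinuation".

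**Related dates.** SAP 11.1 ends days in study at the "date of study completion / discontinuation (or date of last visit if the study completion/discontinuation date is missing"). For subjects who enter with a PGA of 0, SAP 11.7 handles time to first worsening differently: "Subjects who never experience PGA ≥ 2 throughout the study will be censored at the date of their last PGA assessment".

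**The concern.** Censoring should fall no later than the last time at which an event could have been recorded. Beyond that point a subject enlarges the risk set but cannot contribute an event, so the error has one direction: the estimated AESI probability is too low.

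The order of steps in Protocol 4.7 puts the declaration of loss to follow-up after the last contact, possibly by several weeks. The SAP then censors at a discontinuation date without saying which of the two it means, and sites may differ. The last-visit fallback in SAP 11.1 does not help: it applies to days in study, and only when the date is missing.

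Safety is the first-listed objective, and both documents expect high discontinuation. No exposure-adjusted AE rate is planned, so the Kaplan-Meier figures are the AESI output that allows for unequal follow-up. They should not depend on how a site fills in one date.

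**Working it through.** **Inputs from the documents.** 850 enrolled and about 300 completing 40 weeks (Protocol 10.2, SAP 6). So 850 - 300 = 550 leave early, and 550/850 = 64.7%. The plan states no AESI rate, no lost-to-follow-up share and no gap length, so it has no figure of its own to reproduce.

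**Assumptions, not in the documents.**
- Share of discontinuations that are losses to follow-up: p = 10-50%.
- Gap between last AE contact and declaration: g = 4-12 weeks.
- True 40-week AESI risk: 5-30%.
- Constant hazards for the AESI and for discontinuation, independent of each other.

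**Step 1: rates.** Discontinuation: h = -ln(300/850)/40 = 0.02604 per week. AESI at a true 10%: L = -ln(0.90)/40 = 0.10536/40 = 0.002634 per week.

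**Step 2: unobserved subjects kept in the risk set.** At week t, let u = min(t, g). For each subject still under observation, about a(t) = p × (exp(h × u) - 1) lost subjects are still counted. The estimated hazard becomes L/(1 + a(t)).

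**Step 3: example, p = 25%, g = 8.**
- h × g = 0.2083 and exp(0.2083) - 1 = 0.2316, so a = 0.25 × 0.2316 = 0.0579.
- From week 8 on the hazard is multiplied by 1/1.0579 = 0.945. Over the first 8 weeks the average multiplier is 0.973.
- Mean over 40 weeks: (8 × 0.973 + 32 × 0.945)/40 = 0.951.
- Cumulative hazard: 0.10536 × 0.951 = 0.1002, and 1 - exp(-0.1002) = 9.5%, against a true 10.0%.

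**Step 4: simulation over the ranges.** With 400,000 subjects per scenario, the week-40 Kaplan-Meier estimate was computed twice, with lost subjects censored at last contact and at declaration. The table shows the change in percentage points (relative change in brackets).

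| True 40-week risk | p = 10%, g = 4 | p = 25%, g = 8 | p = 50%, g = 12 |
|---|---|---|---|
| 5% | -0.05 (-1.0%) | -0.24 (-4.8%) | -0.64 (-13.0%) |
| 10% | -0.10 (-1.0%) | -0.47 (-4.7%) | -1.28 (-12.7%) |
| 20% | -0.18 (-0.9%) | -0.90 (-4.5%) | -2.50 (-12.3%) |
| 30% | -0.26 (-0.9%) | -1.29 (-4.3%) | -3.55 (-11.8%) |

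Counted risk time rises by about 1% to 14%. The middle cell at 10% agrees with Step 3. Censoring at last contact recovers the assumed risk up to simulation error.

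**Step 5: other exit pattern.** With exits spread evenly over 40 weeks instead, the same example (true 10%, p = 25%, g = 8) gives 9.6%. The result depends little on this choice.

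**Step 6: crude counts.** The number of subjects with an AESI and the number enrolled are the same under both censoring dates, so the crude percentage does not move in any scenario.

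**The case against.** The strongest reply is that the bias depends on a fact the documents do not settle. If the discontinuation date of a lost subject is entered as the last contact, the bias is zero. That stands, and it is why the defect is an undefined date and not a demonstrated understatement.

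A reader might go further than the documents allow in three ways:
- *That AESI incidence as a whole is understated.* The planned incidence is number and percent of subjects, with no person-time denominator, and the censoring date does not touch it. Events that go unseen after contact is lost may lower the crude percentage, but that comes from dropout, and no censoring rule recovers them.
- *That no AE can be reported once visits are missed.* Protocol 4.6.3 and 4.7 require the site to try to reach the subject, and AEs are asked about at any contact. The gap that matters runs from the last such contact, not from the last visit. Protocol 4.6.3 also describes a route to lost-to-follow-up status after one missed rescheduled visit. Eight weeks is therefore one reading, and 12 weeks is only an assumed upper bound.
- *That days in study in SAP 11.1 is wrong for the same reason.* It is a disposition measure. A subject is in the study until considered withdrawn, so the declared date is defensible there.

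The contrast with efficacy is also limited. PGA is scored only at visits, so its last assessment is the natural end of observation, whereas AEs can be reported at other contacts. The contrast shows that the SAP can state a last-assessment rule; it does not prove an inconsistency.

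Finally, the analysis is descriptive and no test depends on these curves. That limits the consequence but does not make an ambiguous censoring date acceptable in a safety figure.

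**Conclusion.** The concern holds in a limited form. SAP 11.11.1 ties censoring in the AESI Kaplan-Meier figures to a date that neither document defines for lost subjects, and Protocol 4.7 allows that date to be a declaration made weeks after the last AE contact. Where the declaration is recorded, the curves are biased downward, by about 1-13% relative at week 40. The upper end needs half of all discontinuations to be losses and a 12-week gap; the middle case moves 10.0% to 9.5%. These sizes rest on the assumed shares, gaps, AESI risks and constant hazards above, and the documents cannot narrow them. The crude AESI tables are unaffected. The effect is modest, but its direction favours the product and the remedy is nearly free, so the SAP should be changed.

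**What to change.** Add one sentence to SAP 11.11.1: AESI-free subjects who are lost to follow-up are censored in the AESI Kaplan-Meier figures at the last visit or contact at which AEs were assessed. This is right whichever date sites record as discontinuation. The days-in-study definition in SAP 11.1 can stay as it is, as a disposition measure.

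The cost is one sentence and a small programming change. No new data collection is needed, because AEs are already asked about at each visit or contact and visit dates are part of the required source data (Protocol 11.1.5). The downside is that the AESI curves may look slightly less favourable.
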